**Not applicable**

Questionnaires described above will be administered in a private setting at the Vermont Lung Center.

**Statistical Considerations:** *Delineate the precise outcomes to be measured and analyzed. Describe how these results will be measured and statistically analyzed. Delineate methods used to estimate the required number of subjects. Describe power calculations if the study involves comparisons. Perform this analysis on each of the primary and secondary objectives, if possible.*

**Analysis Plan.** Baseline comparability between the two randomized arms will be compared using demographic and outcome variables obtained at baseline to identify potential group comparison confounders. Primary outcomes assessed at the end of the study will be compared using a two-sample t-test and associated 95% confidence interval or a Kruskal-Wallis rank test and nonparametric confidence interval if distributional assumptions are of concern. This will be followed by a pre-post repeated measures mixed linear model to test for group specific baseline to follow-up differences, while for those measures observed at multiple time points, a linear mixed model incorporating time at discrete levels will be implemented. The previous t-test comparisons and the mixed models will be extended to covariance models using baseline mROS, age, sex, BMI, smoking history, duration of asthma and asthma medications, and a confounder score using all items. The effect of medications will be determined by using dummy variables for each class of medication, and by using the cumulative dose of inhaled corticosteroid and  $\beta$  agonist in the regression model. We will compare the rate of events describing any change in medications (whether an increase or decrease), including addition of new anti-asthma drugs and use of steroid tapers in the treatment and placebo groups. Missing data patterns from any lost to follow-up or incomplete data collection will be examined using standard approaches to assess missing at random or missing completely at random assumptions. If missing data is of concern, specific multiple imputation approaches for missing data will be implemented. Analyses using complete data and imputed data sets will be qualitatively compared and presented jointly.

**Sample size.** The sample size calculations are based upon estimates of clinically meaningful mean differences and standard deviations derived from our studies of obese asthmatics at the University of Vermont (although this is predominantly a Caucasian population compared with the Duke site, we have found that methacholine reactivity variability does not differ by race [or BMI] in prior studies of the ALA-ACRC). The analysis is based upon a repeated measures analysis of variance approach. The primary outcome is the methacholine responsiveness. We assume that after treatment with MitoQ, a 20% fall in FEV1 will be detected using a mean methacholine dose of 4 mg/ml, an improvement over the baseline estimate of 2 mg/ml. It is assumed that those in the control group will show no improvement over baseline. Using a within-person standard deviation of 3.0, and the assumptions indicated above, 17 individuals per group would provide 80% power with a 5% significance level to detect a difference between patients assigned to active treatment versus placebo. We will inflate these numbers to allow for a 10% patient drop-out and plan to recruit 40 participants total. Pre- and post- changes in mean lung function (% predicted) and questionnaire scores will be compared for each group, and across groups as described previously.

**Data quality.** Data Quality will be enforced through a variety of techniques, and in collaboration with [name] in biostatistics at UVM. This includes the preparation of a detailed manual of operations, staff training and certification of key staff in study procedures, design of unambiguous self-documenting data collection forms, double data entry, audit of source documents against the central database, automated intra-form and inter-form data consistency checks, range and validity checks during data entry, and centralized eligibility checks and randomization assignments. We will have an in-person training meeting at the start of this clinical study for the Investigators and Coordinators at Duke and UVM.

Data quality will be reviewed and discussed at monthly conference calls. [name] will meet in person no less than three times a year at the Steering Committee meetings of the American Lung Association-Airways Clinical Research Center network.

**Risks/Benefits:** *Describe any potential or known risks. This includes physical, psychological, social, legal or other risks. Estimate the probability that given risk may occur, its severity and potential reversibility. If the study involves a placebo or washout period, the risks related to these must be addressed in both the protocol and consent. Describe the planned procedures for protecting against or minimizing potential risks and assess their likely effectiveness. Where appropriate, discuss plans for ensuring necessary medical or professional intervention in the event of adverse effects to the subjects. Discuss the potential benefits of the research to the subjects and others. Discuss why the risks to the subjects are reasonable in relation to the anticipated benefits to subjects and others. Discuss the importance of the knowledge gained or to be gained as a result of the proposed research and why the risks are reasonable in relation to the knowledge that reasonably may result. If there are no benefits state so.*

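### The plan does not say which analysis of methacholine response is primary, or whether its t-test uses end values or change; baseline response and centre are not named covariates

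*Combined protocol and SAP*

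**What the plan says.** The Primary Outcome section defines the outcome as a change in airway reactivity. Under Statistical Considerations, the Analysis Plan sets out three steps:

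1. "Primary outcomes assessed at the end of the study will be compared using a two-sample t-test", "or a Kruskal-Wallis rank test and nonparametric confidence interval if distributional assumptions are of concern". No criterion for switching to the rank test is given.
2. "This will be followed by a pre-post repeated measures mixed linear model to test for group specific baseline to follow-up differences".
3. "The previous t-test comparisons and the mixed models will be extended to covariance models using baseline mROS, age, sex, BMI, smoking history", then duration of asthma, asthma medications "and a confounder score using all items".

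Baseline outcome values are mentioned once more, in a comparability check that uses "demographic and outcome variables obtained at baseline to identify potential group comparison confounders". Medication effects are to be examined with class indicators and "by using the cumulative dose of inhaled corticosteroid and" beta-agonist, with no time window stated. The plan adds: "We will compare the rate of events describing any change in medications".

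The Sample size paragraph rests on repeated measures ANOVA, a rise from 2 to 4 mg/ml on MitoQ with no change on placebo, a within-person SD of 3.0, and 17 per arm for 80% power at 5%. Randomization and blinding stratifies by centre. Methacholine challenge is scheduled at Visits 2 and 5b.

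**The concern.** Three places in the document point to different analyses of one outcome. The Analysis Plan's wording suggests a comparison of end-of-study values. The Primary Outcome section and the sample-size method suggest a comparison of change. The steps come in an order, but none is called primary or supportive, so a reader of the results cannot tell which p-value answers the trial's question.

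Baseline methacholine response is probably the strongest available predictor of end-of-study response, yet it is not a named covariate. It enters the pre-post model as a repeated measure, and could otherwise enter only through the comparability check or the undefined confounder score. Centre, the one stratification factor, does not appear in the analysis plan.

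The stakes are an unsettled result and some lost precision. The trial is a pilot, but its stated primary aim is to find out whether MitoQ improves airway reactivity, and it is meant to inform a decision on a larger trial.

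**Working it through.** **The plan's own figure.** With a difference of 4 − 2 = 2 mg/ml, two-sided 5%, 80% power and (1.96 + 0.84)² ≈ 7.85:

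- End values, SD 3.0: 2 × 7.85 × 9/4 = 35.3, so 36 per arm.
- Change, within-person SD 3.0 (SD of change 3√2 = 4.24): 2 × 7.85 × 18/4 = 70.6, so 71 per arm.
- One-sample change within a single arm: 7.85 × 9/4 = 17.7, so 18.

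The stated 17 is not reproduced by either between-arm formula. That is a separate matter. Here it means only that the sample size does not reveal which analysis was intended.

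**Power by analysis.** The documents give no baseline-to-end correlation, so ρ = 0.3, 0.5 and 0.7 are assumed. With total SD s:

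- end value: SD = s
- change (pre-post): SD = s√(2(1−ρ))
- ANCOVA on baseline: residual SD = s√(1−ρ²)

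Reading 1 takes 3.0 as the total SD. Reading 2 takes it as within-person, as the Sample size paragraph says, so s = 3/√(1−ρ) = 3.59, 4.24, 5.48 and the SD of change is 4.24 throughout. Power is for 17 per arm, two-sided 5%, by simulation (at least 40,000 trials per cell for Reading 1; Reading 2 checked with 60,000).

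| SD reading | ρ | End value | Pre-post | ANCOVA | ANCOVA gain over the better alternative |
|---|---|---|---|---|---|
| Total | 0.3 | 47% | 36% | 49% | about 2 points |
| Total | 0.5 | 47% | 47% | 57% | about 10 |
| Total | 0.7 | 47% | 68-69% | 74% | about 5 |
| Within-person | 0.3 | 35% | 27% | 37% | about 1-2 |
| Within-person | 0.5 | 27% | 27% | 33% | about 6 |
| Within-person | 0.7 | 18% | 27% | 30% | about 3 |

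**With a ceiling.** The listed methacholine concentrations stop at 4 mg/ml. On a log2 scale with a one-doubling effect, latent baseline mean 2 mg/ml, baseline truncated at 4 and end values capped at 4:

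- SD 1.5: end value 43/47/52%, pre-post 29/38/58%, ANCOVA 44/51/68% at ρ 0.3/0.5/0.7.
- SD 2.0: end value 26/29/33%, pre-post 18/24/37%, ANCOVA 26/32/44%.

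The ANCOVA gain is about 0, 2-5 and 7-10 points, including runs at a latent mean of 4 mg/ml. Truncating baseline at 4 is a simplification, because the inclusion criteria also admit on oscillometry.

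**Do the end-value and pre-post tests agree?** With the planned effect, verdicts differ in 31/34/41% of trials on the total-SD reading, in about 27-28% on the within-person reading, and in 22-36% under the ceiling. With no effect, at least one of the two has p<0.05 in about 9% of trials, against 5% for one named test.

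**If the t-test uses change.** With complete two-visit data, the arm-by-time test in a random-intercept model gave the same statistic as the t-test on change in all three data sets tried. The disagreement and the 9% then do not arise for this pair.

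**Centre.** Assume ρ = 0.5, 18 + 16 patients, and a centre difference of 0 to 1 SD. Leaving centre out of the end-value t-test gives type I error of 2.9-5.0% if arms are balanced within centre and about 5% under simple randomisation. Once baseline is in the model, adding centre changes power by about −1 to +2 points.

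**The case against.** The best case for the plan has several parts.

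*The analyses are ordered.* The t-test is attached to the primary outcomes, the mixed model follows, and both are then extended. A reader might infer that the list is wholly unranked; that goes too far. What is missing is a label of inferential status. Nor does first place settle it, because an end-value t-test matches neither the change outcome nor the sizing method.

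*The t-test may be a test of change.* Since the primary outcome is defined as change, an outcome assessed at the end could mean change as measured at the last visit. This reading stands as possible. A reader might infer two competing tests with a 9% error rate; the documents establish only an ambiguity, with that consequence on one of its two readings.

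*Baseline is not ignored.* It is in the pre-post model, and baseline outcomes are screened as possible confounders. This stands. But the screen has no stated rule, and a repeated measure in an unconstrained model does not give the precision of ANCOVA.

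*The disagreement rate partly reflects low power.* This also stands: with no effect the two tests differ in only about 7.5-9% of trials.

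*Centre and medication are small matters.* Omitting centre does not inflate type I error, and its effect on power is slight. A reader might infer that adjusting for medication dose distorts the treatment effect. The documents do not say that the dose is on-study use, and the t-test and unadjusted mixed model contain no such term.

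**Conclusion.** The point holds as a gap in specification plus a near-free gain in precision. The plan does not name a primary analysis of methacholine response, does not say whether the t-test uses end values or change, and names neither baseline response nor centre as a covariate. The documents do not support the stronger conclusion that a listed test is invalid or the unadjusted effect biased.

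The possibility of conflicting verdicts is conditional on the end-value reading. The precision gain rests on assumed correlations: about 2/10/5 points if 3.0 is the total SD, about 1-2/6/3 if it is within-person as written, and about 0 to 10 under the 4 mg/ml ceiling. ANCOVA had at least as much power as either alternative in every power comparison shown, but at low correlation the advantage is negligible. The unbounded cases are illustrative, since an SD of 3.0 cannot arise from values confined to 0-4 mg/ml (the maximum is 2). Centre belongs in the model because randomisation is stratified by it, not because omitting it does much harm. The medication-window point is minor and no size is claimed for it. This should be fixed, but it does not invalidate the trial.

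**What to change.** Name one primary analysis: an ANCOVA, or a mixed model constrained to equal baseline means, of end-of-study methacholine response on arm, baseline methacholine response and centre. State the scale (for example log2) and how participants with no response at 4 mg/ml are scored. Label the t-test, the unadjusted pre-post model and the other covariance models as supportive. If a rank-based fallback is kept, state when it applies. As a minor addition, state the window for cumulative medication dose and label any model containing on-study dose exploratory.

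This changes analysis-plan wording only. Methacholine response is already measured at Visits 2 and 5b, and centre is known. The cost is one or two degrees of freedom, with little or no gain if the baseline-to-end correlation is low. Under simple randomisation with no centre difference, including centre costs about one power point.

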**Drug (s)**

**Not applicable**

*Drug name – generic followed by brand name and common abbreviations. Availability – Source and pharmacology; vial or product sizes and supplier. If a placebo will be used, identify its contents and source. (attach investigational drug brochure)*

**Mitoquinol and placebo** will be supplied by MitoQ Ltd, (based in Auckland, New Zealand).

Name and Product. MitoQ™ (Mitoquinol mesylate) capsules

Active ingredient: Mitoquinol mesylate, inactive ingredients microcrystalline cellulose, tapioca, silica dioxide  
Product will be supplied as 20 mg capsules and matching placebo.

**Methacholine** will be purchased as Provocholine® (methapharm) containing 100 mg in 20 ml vials

*Preparation: Reconstitution instructions; preparation of a sterile product, compounded dosage form; mixing guidelines, including fluid and volume required. Identify who will prepare.*

**MitoQ** Product will be supplied as 20 mg capsules and matching placebo.

**Methacholine** will be reconstituted according to the FDA approved package insert. Dosing of methacholine for this study will be: 0.03125 mg/mL, 0.0625 mg/mL, 0.1250 mg/mL, 0.25 mg/mL, 0.5 mg/mL, 1 mg/mL, 2 mg/mL, 4 mg/mL. Solutions will be prepared using Provocholine® 100mg in 20mL Diluent will be 0.9% Normal Saline.

*Storage and stability – for both intact and mixed products.*

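### The primary methacholine response is measured on a two-fold ladder ending at 4 mg/mL, but the plan names neither a log scale nor a rule for results above the top step

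*Combined protocol and SAP*

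**What the plan says.** The Sample size paragraph of Statistical Considerations states: "The primary outcome is the methacholine responsiveness". It assumes that, after treatment, a 20% fall in FEV1 will be "detected using a mean methacholine dose of 4 mg/ml, an improvement over the baseline estimate of 2 mg/ml". For the other arm, "It is assumed that those in the control group will show no improvement over baseline". The calculation continues "Using a within-person standard deviation of 3.0", with no unit, and concludes that "17 individuals per group would provide 80% power with a 5% significance level". It is described as a repeated-measures analysis of variance.

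The Analysis Plan says that end-of-study primary outcomes are "compared using a two-sample t-test and associated 95% confidence interval or a Kruskal-Wallis rank test and nonparametric confidence interval". The rank option applies when distributional assumptions cause concern. A pre-post mixed linear model follows, and then covariance models. The covariates listed include baseline mROS, age, sex, BMI and medication, but not baseline methacholine response. No transformation appears anywhere.

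The methacholine preparation text under Drug and Device Information gives the concentrations: "0.03125 mg/mL, 0.0625 mg/mL, 0.1250 mg/mL, 0.25 mg/mL, 0.5 mg/mL, 1 mg/mL, 2 mg/mL, 4 mg/mL". Inclusion criterion 3 admits a participant whose spirometry or oscillometry result is at or below 4.0 mg/ml at visit 2. The documents do not say what value is recorded for a participant who has no 20% fall at the top step.

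**The concern.** Each step of the challenge is a ratio, so a treatment effect on reactivity is naturally a number of doublings. The only scale the plan gives is mg/ml. If the linear models are run on that scale, the same one-step improvement counts very differently according to where a participant starts. The estimated mean difference then rests mainly on the mildest reactors.

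The trial randomizes 40 people and has one primary outcome. If the scale and the value for results above 4 are settled only after the data are seen, both are open analyst choices on that outcome, and one of them can move power noticeably in either direction.

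**Working it through.** **1. The plan's own figure.** From Sample size: difference 4 − 2 = 2 mg/ml, SD 3.0, 80% power, 5% (two-sided assumed). For two arms, n per arm = 2(1.96 + 0.84)² × SD²/difference² = 2 × 7.85 × 9/4 = 35.3, so 36 (37 with the t distribution).
- If 3.0 is the SD of one measurement around a person's own level, the change has SD 3.0 × √2, and n = 2 × 7.85 × 18/4 = 70.6, so 71.
- The stated 17 is therefore not reproduced. At 17 per arm with SD 3.0, power is about 49% (47% by t).
- The one-sample paired formula gives 7.85 × 9/4 = 17.66, which is close to 17 but does not compare two arms.
- By the t distribution, 17 per arm needs an SD of about 2.0 for a difference of 2.

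**2. Can 3.0 mg/ml describe values on this ladder?** Values between 0.03125 and 4 have an SD of at most (4 − 0.03125)/2 = 1.98. So 3.0 cannot be the SD of recorded mg/ml values unless results are recorded above 4. Similarly, if non-reaction is recorded as 4, a treated mean of 4 requires every treated participant to be at the ceiling.

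**3. Weight of one step.** Raw: 4 − 2 = 2 and 0.25 − 0.125 = 0.125, a ratio of 2/0.125 = 16. On log2 both steps equal 1.

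**4. Power, log2 minus raw.** Simulated trials used 18 per arm (40 less 10% drop-out), a true effect of one doubling and baseline at or below 4 mg/ml. Assumed, because the documents give no SD in doublings: log-normal reactivity, between-person SD 1 to 2 doublings and test-retest SD 0.7 to 1.0. With complete data at two time points, the change score is equivalent to the pre-post mixed model.

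| Analysis | Above 4 recorded as 4 | Above 4 recorded as 8 |
|---|---|---|
| End-of-study t-test | −1 to +3 points | +5 to +11 |
| Change score | −8 to +13 | +1 to +26 |
| Baseline-adjusted | +1 to +17 | +8 to +28 |

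A wider assumed grid used geometric mean 0.5 to 2 mg/ml, between-person SD 0.75 to 2.0 and within-person SD 0.5 to 1.5:

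| Analysis | Above 4 recorded as 4 | Above 4 recorded as 8 |
|---|---|---|
| End-of-study t-test | median 1 to 2 (range −6 to +9) | median 3 to 7 (−6 to +18) |
| Change score | median 1 (−10 to +19) | median 3 to 11 (−8 to +36) |
| Baseline-adjusted | median 4 to 5 (−2 to +22) | median 9 to 16 (0 to +38) |

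Without any ceiling, baseline-adjusted power was 77% raw against 88% log2 with a narrow spread, and 30% against 55% with a wide one. The protocol's ladder does not allow that situation.

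**5. Power if the plan is restated in doublings.** With one doubling and 17 per arm, by the t distribution, power is 81% if the SD of the analysed quantity is 1.0 doubling, 47% at 1.5 and 29% at 2.0. For a change score that SD is √2 times the within-person SD: 0.7 gives 0.99 and 1.0 gives 1.41.

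**The case against.** **The plan never says that the analysis is in raw mg/ml.** This is correct. Planning units do not specify an analysis, and a reader should not take the text as a commitment to the raw scale. What stands is that mg/ml is the only scale given and the stated power rests on it.

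**The rank test already deals with skew.** In part it does. Ranks are the same in mg/ml and in log2. With unbounded log-normal values (mean 2, SD 3) and 17 per arm, simulated power was 29% for the raw t-test, 43% for the rank test and 44% for the log2 t-test. But the trigger is undefined, and the fallback covers only the first unadjusted comparison.

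**The ladder's ceiling removes most of the skew.** This is the strongest objection, and it limits the point. A reader might infer that the planned t-test loses substantial power. That needs a right tail well above 4 mg/ml, which the ladder does not record. With results above 4 set to 4, raw and log2 t-tests are nearly equal, and raw can win for the change score (81% against 73%, and 52% against 44%, in two narrow-spread settings). The ceiling and the scale therefore cannot be treated as separate questions.

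**The planning figures do not prove skew.** A normal variable with mean 2 and SD 3.0 falls below zero 25% of the time, which may look like evidence. But the 3.0 has no unit, is called within-person, and cannot be the SD of values on this ladder. It points to a doubtful sample-size input.

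**The largest gains belong to a model the plan does not list.** This is fair. Baseline methacholine response is not among the named covariates, so the pre-post model is the closest listed analysis. The baseline-adjusted gain becomes available only if that comparison is added.

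**Conclusion.** The point holds as an under-specified analysis that is cheap to improve. The plan should fix the scale and the treatment of results above 4 mg/mL together. Log2 matches how the response is measured and gives every step equal weight. It usually raises power for a baseline-adjusted model: by about 8 to 28 points if results above 4 are recorded as 8, and about 1 to 17 if recorded as 4. For the end-of-study t-test the gain is about 5 to 11 points in the first case and near zero in the second. For the change score it runs from 1 to 26 points in the first case and from −8 to +13 in the second.

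These ranges rest on assumed variability in doublings, log-normal reactivity and a one-doubling effect. They show direction and order of size and do not predict this trial's power. The 16-to-1 weighting, the missing trigger and the missing rule above 4 do not depend on those assumptions. The documents do not support a general claim that the planned t-test is badly underpowered because of its scale.

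**What to change.** In the Analysis Plan:
- State that the concentration giving a 20% fall in FEV1 is analysed as log2 in every between-arm model.
- Add a comparison adjusted for log2 baseline.
- Report the arm difference in doublings with a 95% confidence interval, back-transformed to a ratio.
- Make the rank test a fixed sensitivity analysis, so that it is not a switch made after seeing the data.
- State in the same place how a result with no 20% fall at 4 mg/mL is analysed, for example as right-censored or set one doubling above the top step. Apply the rule at baseline too: inclusion criterion 3 also admits on oscillometry, so some participants may have no spirometry value at entry.

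In Sample size, restate the effect as one doubling, give the within-person SD in doublings from the University of Vermont data already cited, and restate the resulting power.

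The change needs no new participants, visits or measurements. It costs a little more analysis work, mainly for the censoring rule, and the restated power may be less favourable than 80%.

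### The adjusted end-of-study model lists many covariates, fixes neither their number nor their joint use, and leaves out the outcome's baseline value and center; entered together on 34 to 36 completers they would probably cost precision.

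*Combined protocol and SAP*

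**What the plan says.** All of this is in the Statistical Considerations section, except the stratification.

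- The Analysis Plan puts an unadjusted comparison first: "Primary outcomes assessed at the end of the study will be compared using a two-sample t-test", with a rank test as fallback. A "pre-post repeated measures mixed linear model to test for group specific baseline to follow-up differences" follows.
- Both are then adjusted: "The previous t-test comparisons and the mixed models will be extended to covariance models". The covariates are "baseline mROS, age, sex, BMI, smoking history, duration of asthma and asthma medications, and a confounder score using all items".
- Medications are handled "using dummy variables for each class of medication" and "by using the cumulative dose of inhaled corticosteroid and" β agonist.
- The arms are also compared at baseline "to identify potential group comparison confounders".
- The Sample size paragraph gives 17 per group, allows 10% drop-out, and states a "plan to recruit 40 participants total".
- Randomization and blinding stratifies assignment by center.

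The plan does not say how many medication classes there are, whether dummies and doses are used together or as alternatives, or whether the score joins its items or replaces them. Neither center nor the baseline value of the outcome is on the covariate list.

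**The concern.** In a randomized trial, a baseline covariate improves precision if it predicts the outcome. If it does not, it uses a degree of freedom and adds chance correlation with treatment, and the interval widens. With fewer than 40 completers that cost builds up quickly. The list here is long and open-ended, yet it lacks two covariates with a clear claim to a place: the outcome's baseline value, usually the strongest predictor, and the stratification factor.

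Two things are at stake. The adjusted estimate may be less precise than the unadjusted one it is meant to support. And because the covariate set is not fixed, several different adjusted estimates are all compatible with the text, so an adjusted result that disagrees with the unadjusted one would be hard to interpret.

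**Working it through.** **Number analyzed.** 17 per group is 34. Recruiting 40 with 10% drop-out leaves 40 × 0.9 = 36. The inflation itself is consistent: 34/0.9 = 37.8, so 38, below the planned 40. The 17 per group does not follow from a plain two-sample formula (difference 2, SD 3.0 gives 36 per group), but that is a separate question; 34 is used here only as a count. The plan states no covariate count and no precision for the adjusted models, so there is no figure of its own to reproduce on this point.

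**Number of terms, k.** Six named items, one degree of freedom each if continuous or binary; two cumulative-dose terms; one score; and the class dummies. The number of classes is not given, so I assume 2 to 6:

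- six items and two doses only: k = 8
- everything, 2 classes: 6 + 2 + 1 + 2 = 11
- everything, 6 classes: 6 + 2 + 1 + 6 = 15

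**Formula.** For k baseline covariates independent of a 1:1 assignment, with n analyzed and a fraction R² of outcome variance explained,

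Var(adjusted)/Var(unadjusted) = (1 − R²) × (n − 3)/(n − k − 3).

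Setting this to 1 gives the break-even R² = k/(n − 3). The interval ratio at R² = 0 is the square root of the variance ratio times t(0.975, n − 2 − k)/t(0.975, n − 2).

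| n | k | Variance ratio, R² = 0 | 95% CI width ratio, R² = 0 | Break-even R² |
|---|---|---|---|---|
| 36 | 2 | 33/31 = 1.06 | 1.034 | 6.1% |
| 34 | 2 | 31/29 = 1.07 | 1.037 | 6.5% |
| 36 | 8 | 33/25 = 1.32 | 1.162 | 24.2% |
| 34 | 8 | 31/23 = 1.35 | 1.176 | 25.8% |
| 36 | 11 | 33/22 = 1.50 | 1.247 | 33.3% |
| 34 | 11 | 31/20 = 1.55 | 1.271 | 35.5% |
| 36 | 15 | 33/18 = 1.83 | 1.395 | 45.5% |
| 34 | 15 | 31/16 = 1.94 | 1.442 | 48.4% |

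Simulation agrees: at R² = 0 the variance ratio was 1.81 for n = 36, k = 15 and 1.95 for n = 34, k = 15. Requiring equal interval width instead of equal variance raises the break-even a little, for example to 51.9% at n = 34, k = 15.

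**The score.** If it is a linear function of items already in the model, it adds no information. A simulated design with intercept, treatment, 13 items and such a score had 16 columns and rank 15. The effective k is then 10 to 14, with break-even from 10/33 = 30% to 14/31 = 45%. Entered alone (k = 1), the score has a break-even of about 3%.

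**The mixed model.** With complete pre-post data the group-by-time term is the difference in mean change, and a time-invariant main effect cancels from each person's change. In one simulated data set (36 participants), adding 13 such covariates left the estimate at 0.656 and its standard error at 0.386. The table therefore applies to the covariance extension of the t-test only.

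**The case against.** The strongest reply is that the plan never commits to the large model. Dummies and cumulative doses can be read as two ways of representing medications, and a single score is a recognized way to compress many covariates into one. Used alone, it costs almost nothing. The inhaled corticosteroid dummy would be nearly constant, since Background Asthma Care has everyone prescribed that class. All of this stands, and it is why the size is given as conditional. It also confirms the gap: readings needing anywhere from 3% to 48% explained variance all fit the same sentence.

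The unadjusted test comes first, and the pre-post model already uses the baseline measurement as a response. A reader might infer that the trial's power collapses or that every adjusted estimate loses precision. The documents do not support either: the loss is confined to one supporting analysis. Nor is that analysis invalid. With true baseline covariates the adjusted linear estimate stays unbiased and its interval reflects the lost degrees of freedom.

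A reader might also infer that covariates will be picked by baseline imbalance. The plan says it will look for confounders that way, but states no selection rule and lists its covariates in advance. What remains is that the purpose of the baseline comparison should be made clear.

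Multiple imputation is planned if missing data are of concern. Treating all 40 as analyzed lowers the break-even for k = 11 to 15 to 11/37 = 30% and 15/37 = 41%. That is smaller, but the same problem.

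Finally, this is a pilot, and exploratory adjustment is reasonable in a pilot. That argues for labeling such models as sensitivity analyses, which the fix does.

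**Conclusion.** The point holds as a conditional precision problem and a specification gap. If all listed terms enter one end-of-study ANCOVA on 34 to 36 completers, they must explain about 33% to 48% of outcome variance to avoid losing precision. The six items and two dose terms alone need 24% to 26%, and if they explained nothing the interval would be 16% to 18% wider. A score linear in its items is a collinearity fault when entered with them, not an extra degree of freedom.

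The figures assume 2 to 6 medication classes, one degree of freedom per named item, and covariates measured at baseline and independent of assignment. If cumulative dose accrues during the trial it is measured after randomization, and possible bias becomes a separate question. A firm count of covariates cannot be read from the documents.

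A short, prespecified adjusted model would be better at almost no cost, so the change is worth making even though the analysis is a supporting one.

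**What to change.** In the Analysis Plan:

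1. Prespecify the adjusted end-of-study model as treatment, the outcome's own baseline value, and center.
2. Do not enter the confounder score in a model that also contains its items.
3. Show the other listed baseline covariates only as sensitivity analyses, one at a time or through the score alone.
4. State that the baseline comparison of arms is descriptive and does not select covariates.

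The two prespecified covariates use data already collected. Even if they explained nothing, they would widen the interval by only 3% to 4% (k = 2 in the table), and they pay for themselves once they explain about 6.5% of the variance. The cost is a wording change. The small downside is that no single model carries every listed covariate.
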